## INVESTIGATOR STUDY PLAN – Take a Break (H00007427)

review of popular relaxation or meditation Apps currently available on iTunes. We found ten Apps relevant to our review. The most popular used a combination of guided deep breathing and sounds to induce relaxation. Relaxation through deep breathing has been used in smoking cessation, and we will use these popular and evidence-supported principles. We have identified 3 free apps that can be used to help relax during a smoking craving. They are:

- *Take a Break*: This app is designed to walk the participant through a guided breathing exercise to help with relaxation.
- *Calm*: This app can help the participant relax their whole body through a series of auditory guided breathing and relaxation exercises.
- *Breathe2Relax*: For this app, the participant can watch and participate in a series of demonstrations to help them relax. These include: diaphragmatic breathing, learning about stress, and engaging in reading, writing, and practicing different types of relaxation.
- “*Smoker 2 Smoker*” Motivational Messages: Our team has developed and evaluated a computer-tailored motivational messaging system. Messages were evaluated within the context of a web-assisted tobacco intervention (R21-CA089011, 1R01CA129091-01). Expert-written messages were developed through a group review, and were guided by current guidelines and Social Cognitive Theory. Smoker-written messages were written by current smokers responding to scenarios that varied on readiness to quit smoking. We have demonstrated that the messages increased engagement in the online smoking intervention and increased six-month smoking cessation outcomes. As with the other mini-games, smokers will receive points for viewing the messages. Smokers can also receive bonus points by writing their own messages.
- *Challenge Quizzes*: These brief games will consist of 1 to 3 questions with multiple-choice answers. The purpose of the Quizzes is two-fold: 1) to impart tailored feedback (brief educational messages designed to change perceptions about smoking cessation); and 2) to assess situational characteristics, abstinence behaviors, and cravings. Smokers will have up to 3 Quizzes per day. Players will receive increasing points for the number of consecutive reports, regardless of abstinence or lack of abstinence.

### Take a Break 3-week Marathon & Longitudinal Access:

- *Week 1 TRAINING Challenge*: The purpose of the Training Challenge is to collect information about

smokers' daily life experiences. Smokers may think about challenges they may encounter when they “Break” with smoking. Players will earn points by completing Challenge

Quizzes. In addition to providing data, the use of the Challenge Quizzes will provide smokers experience with interacting with the game so they will be better prepared to “Take a Break.” At the

## INVESTIGATOR STUDY PLAN – Take a Break (H00007427)

completion of the Training Challenge, players will be asked to set a goal for number of days abstinent during the Break challenge.

- *Week 2-3 The BREAK NRT-sampling experience and mHealth tools:* The Break is a two-week experience. During the Break, smokers are encouraged to initiate abstinence from smoking and maintain abstinence for as long as possible. Consistent with a motivational intervention, smokers will not be forced to initiate abstinence on the first day of their assigned Break period, but will earn points for each day they reply to the ecological momentary assessment through our two-way texting system. During the Break, smokers will be supported by our evidence-based and effectiveness-tested mobile health tools in the Game. At the end of the Break, players will meet once more with our study staff. All Intervention participants will receive gold, silver, or bronze level awards for participation and will be asked if they would like to set a quit date. Current smoking will be determined through self-report and verification with a carbon monoxide breath monitor. Smoking cessation verification will be performed at the study site they were recruited at during the participant's last in-person session.

*Take a Break Game Longitudinal Access:* After the immediate skills-building experience, smokers in the intervention group will have access to the game during the 6-month follow-up period. This access includes motivational text messages sent from a toll-free number ([name]), distraction and relaxation apps, and access to the study TTS. Thus, once they are ready for a future quit attempt, these intervention tools will be available to them. Smokers who have already completed a Take a Break experience may then choose to join new challenges, trying additional abstinence periods. Thus, the initial 3-week experience period serves as an intervention itself, and as a practice use of the game so that the smoker will be better prepared for the next quit attempt. NRT will not be provided by investigators after the first 3-week experience. Upon completion of study participation after the 6-month follow-up visit, participants (both Intervention and Control) will be asked if they are interested in participating in future research activities. Interested participants will be asked to sign an authorization to contact form (See TAB.authorization\_to\_contact.7.19.17). To increase engagement with intervention tools after the 3-week follow-up, we will send an additional texting assessment to intervention participants. These smokers will be asked to rate their current mood using the question, "How would you rate your mood right now?" Participants will be prompted to reply based on the response options "1= good, 2=ok, or 3= bad". We will ask this question for a period of 5 weeks, twice a week for a total of 10 assessments. Following this assessment, study participants will be randomly asked whether they would like to speak to the TTS or reminded to utilize the distraction or relaxation mobile apps previously downloaded.

- For study participants unable to come in person to complete the 6- month follow-up visit, we will mail a letter [see "Request to complete\_TAB\_6mo\_fuvisit"] asking them to complete the 6 month follow up survey and mail back in the included pre-postage envelope.

### NRT-Sampling (provided to both intervention and comparison groups):

During the initial recruitment session, we will provide smokers' 1 box (81 Nicorette4-mg mint) of nicotine lozenges purchased over the counter from a commercial vendor. Participants can choose to use or not to use the NRT. It will be provided to participants, but use of it is optional. (See Section #32 for details on dispensing procedures.)

[figure not shown]
Quality Improvement Interviews: The researchers would like to interview UMass Memorial nurses and hospital leadership to better understand the current initiatives related to tobacco cessation in the hospital setting and how a quality improvement mobile health tool for tobacco cessation could enhance care for current tobacco users staying at the hospital. The purpose of interviewing hospital leadership is to gather insight into current tobacco cessation initiatives and their insight into whether this tobacco cessation tool could improve the quality of care given to tobacco users admitted to the hospital. We will interview 10

## INVESTIGATOR STUDY PLAN – Take a Break (H00007427)

people in hospital leadership at UMass Memorial. The purpose of interviewing nurses would be to understand more fully the work they currently perform on their hospital floor, how they identify tobacco users on admission, the actions taken to assist tobacco users during their hospital stay and their insight as to whether this tobacco cessation tool would benefit tobacco users in the hospital. We will interview 20 nurses at UMass Memorial.

[figure not shown]
Participants will be interviewed for approximately 45 minutes and will be audio-recorded. The interviewer will remind participants that the interview is being audio-recorded and as a measure to protect your confidentiality, they will be asked not to mention their full name once the interview recording starts. Participants will give verbal consent and will be given a Fact Sheet for their records. They will be reminded that the data will be protected and should data be lost or stolen, it poses minimal risk to participants. The recorder will be stored in a locked drawer, the data will be protected in the password-protected PI's UMass Medical QHS department folder, and the data will be destroyed at the end of the study. The participants will be compensated for their time with a \$50 Amazon gift card. Funds from a training grant funded by NCI for post-doctoral fellows in Cancer Research are being utilized for the incentives of the Quality Improvement Interviews. As part of the training grant's budget, each fellow is awarded funding to conduct their own research. The research & human subjects portion of the grant are not provided in section 7.0 because the grant does not provide the specifics of the research activities.

Below are timelines of the events for each study aim. Described in the timeline are the events that will occur at each of these study points.

## INVESTIGATOR STUDY PLAN – Take a Break (H00007427)

### Take a Break Study Timeline by Study Aim (2 &3)

## INVESTIGATOR STUDY PLAN – Take a Break (H00007427)

### 11) Data and Specimen Banking

Data collection for this project includes web-based, telephone, and in-person methods for Aims 1, 2, and 3. (Table 3). All primary study data collected will be centralized and stored within the UMMS Regulated Environment. Paper copies of consent forms and data collection tools (baseline and follow-up surveys) will remain at the study-specific sites in a locked cabinet. Only CITI trained study staff will be able to access to primary study data. Data files cannot be transferred electronically outside of the regulated environment.

**Aim 1: Usability think-aloud interviews.** We will conduct usability interviews using the Morae software and laptops with full data encryption. The Morae recording will be transferred to a server in the UMMS IS regulated environment and removed from the laptops.

**Aim 1 + 2: Mini Pilot + RCT.** Surveys conducted on the telephone and in-person (see Table 3 for specific surveys) will be recorded within REDCap at the time of completion. TAB activity will be collected by UMMS web-based servers and stored within the UMMS IS regulated environment.

Table 3: Data Collected and Source

Variable	Source		Stage of Collection					
	EHR Registry	Baseline	App Metrics	Follow Up	Screening	Baseline	Intervention	Follow Up
Demographics (age, gender, race)	Y	Y	N	N	Y	Y	N	N
Level of Addiction (FTND)	N	Y	N	N	N	Y	N	N
Past Quit History	Y	Y	N	N	N	Y	N	N
Readiness to Quit	N	Y	N	Y	Y	Y	N	N
SES/Housing Stability	N	Y	N	N	N	Y	N	N
Depression (CES-D)	N	N	N	N	Y	N	N	N
Alternative Tobacco Use & e-cig	N	Y	N	Y	N	Y	N	Y
NRT Use	Y	Y	N	Y	Y	Y	N	Y
Alcohol/Illlicit Drug Use	N	Y	N	Y	N	Y	N	Y
Smoking in Household	N	Y	N	N	N	Y	N	N
Cessation Treatment Beliefs	N	Y	N	Y	N	Y	N	Y
Health Behaviors (exercise, sleep diet)	N	Y	N	Y	N	Y	N	Y
Health Literacy	N	Y	N	N	N	Y	N	N
Medical Comorbidities (SCQ)	Y	Y	N	N	Y	Y	N	N
Perceived Stress	N	Y	N	Y	N	Y	Y	Y
Provider Behavior	N	Y	N	N	N	Y	N	N
Religion	N	Y	N	N	N	Y	N	N
Self-efficacy (SEQ-12)	N	Y	N	Y	N	Y	N	Y
Smoking Urges (QSU)	N	N	Y	Y	N	N	Y	Y
Social Support/Family (mMOS-SS)	N	Y	N	N	N	Y	N	N
Technology Literacy	N	Y	N	N	N	Y	N	N
Triggers	N	Y	N	N	N	Y	N	N
Challenge Quiz Completion	N	N	Y	N	N	N	Y	N
Days Abstinent	N	N	Y	N	N	N	Y	N
Smoking Cessation*	N	N	N	Y	N	N	N	Y
(biochemically verified a 3wk, 6 months)								
Time to First Quit Attempt	N	N	N	Y	N	N	N	Y
Use of Apps/Mini-Games	N	N	Y	Y	N	N	Y	Y

**Aim 3: Follow-Up.** Surveys conducted during follow-up will be stored in the same manner as in Aim 1 and 2. Biochemically verified smoking cessation results will be stored in REDCap. Biochemically verified smoking cessation tests will only be conducted with participants that used the optional NRT.

**Quality Improvement Interviews:** Participant interviews will be audio-recorded. The interviewer will remind participants that the interview is being audio-recorded and as a measure to protect their confidentiality, they will be told not to mention their full name once the interview recording starts. They will be reminded that the data will be protected. In the unlikely event that the data is lost or

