### 3) Objectives

Take a Break (TAB) is a randomized trial designed to evaluate Nicotine Replacement Therapy (NRT)-sampling and a mHealth suite of apps. TAB is a time-limited self-efficacy and skills building experience for Motivation Phase smokers. TAB is designed to create a timeline within which motivation smokers will be encouraged to try a brief period of abstinence. Smokers in this Motivation Phase are relatively untapped in research available information. This project offers these smokers point-of-need technology support in the many components of the intervention.

Our Specific Aims are

[figure not shown]
- AIM 1: Refine the Take a Break mHealth tool and implementation program.
- AIM 2: Conduct a randomized trial of the effectiveness of Take a Break.
- AIM 3: Follow participants in the AIM 2 randomized clinical trial for 6 months to evaluate time to quit attempts, number of quit attempts, and 6-month biochemically verified point prevalent cessation.

The Take a Break intervention is designed to increase self-efficacy and support new skills for Motivation Phase smokers. We hypothesize that, compared with the NRT-only group, the Take a Break group will have a greater number of days abstinent during the ‘break’ period, a greater increase in self-efficacy at the end of the ‘break’ period, a lower time to first quit attempt, and a higher rate of quit at 6 months. This research study will also provide valuable insight into this population of smokers and increase our understanding of which tools may be effective in helping them quit smoking.

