## INVESTIGATOR STUDY PLAN – Take a Break (H00007427)

of instantaneous probability of an event in the two groups. A positive hazard ratio implies that the intervention group will have a shorter time to quit than the control group. We will express the risk estimates as hazards ratios, 95% confidence intervals, and p-values. As with the previous aims we will also assess model fit.

- Hypothesis 4: Point prevalent cessation measured at 6 months will be greater in the Take a Break intervention than in the control group. The main dependent variable is patient tobacco cessation rate. The primary independent variable is assignment to intervention or control group. We have designed a patient-level analysis around point prevalence cessation based on the following question “Do you currently smoke cigarettes (smoked even 1 puff in the last 7 days)?” We will use a two-sided chi-square test for equality of proportions to test whether the quit rates differ between the groups. If we need to adjust for any covariates, we will include them in a multivariable logistic regression model with smoking cessation as the outcome and group status as the main independent variable. Using mediation analysis, we will examine the potential mechanisms through which we anticipate the intervention may produce a beneficial effect.

Power Analysis: We will make every effort to maximize participant retention in the study. For our short-term evaluation, we do not expect high rates of attrition; however, we approximate that there will be about 15-20% attrition based on previous studies. Thus, although we plan to randomize 500, our power calculations for outcomes are based on 400 completing follow-up. We will monitor recruitment and retention, and inflate our sample as needed to achieve the resulting sample of 400 completing 6-months. We will estimate potential bias due to dropouts in our study and perform a series of sensitivity analyses to understand the extent of this bias. We will assess the extent of missing data by treatment group for each time point. Power calculations are based primarily on the two primary hypotheses (H1 and H3) and were conducted in the statistical software PASS. Again, power calculations are based on 400 subjects with complete data (even though we plan to randomize 500).

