## INVESTIGATOR STUDY PLAN – Take a Break (H00007427)

- Hypothesis 4: We assumed a control cessation rate of 15%, 48 a two-sided significance level of 0.05. A sample size of 200 in each group will achieve 80% power to detect a difference of 11% (quit rate in the intervention=26%) in quit rates between the two groups. This is based on a Z-test with pooled variance.

Data Security: We will handle data differently for UMMS, Northwell Health, VACWM and RMG smokers, per each institution's protocol. UMMS and RMG are covered under the same UMMS IRB docket while Northwell Health and VACWM have protocols independently reviewed by their own IRB. Table 4 summarizes data collection. There will be no transfer of patient data between study sites and UMMS prior to recruitment into study. Screening data collected for recruitment will be password protected and stored behind each study site's firewall. Patient contact information provided through the eRefer portal will be encrypted at rest and during transit using Secure Sockets Layer (SSL) standard security protocol. Each study site will have access to only its own identifiable patient data with the exception of UMMS study staff which will have access to all participant identifiable data. Once smokers are enrolled in the study, their intervention data will be stored on UMass servers. This will be done by entering the data directly into the UMMS REDCap database by study staff at each study site. This data will be stored in the regulated database servers and accessible through a secure form and a password-protected connection.

Table 4: Data Collection Source and Storage

Source	Collected From	Personal Identifiers	Collected By	Data Storage
Aim 1				
Think Aloud Usability	Smokers participating in the usability sessions at UMMS Technology usability lab	Yes (identifiers are collected and stored in encrypted form)	UMMS database server in the regulated environment	UMMS IS regulated environment
Mini pilot	Mini Pilot will match Aim 2 data collection plus an additional qualitative interview	Yes (identifiers are collected and stored in encrypted form)	See Aim 2 procedures. Qualitative interviews are directly entered into the regulated environment through a secure REDCap form	UMMS IS regulated environment
Aim 2 Recruitment				

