## INVESTIGATOR STUDY PLAN – Take a Break (H00007427)

### 32) Drugs or Devices

The NRT used in this study is not investigational, and therefore, does not have an IND. The NRT being used in this study is IND exempt since it meets the following criteria: 1) The drug is lawfully marketed in the United States; 2) The investigation does not involve a route, dosage level, or use in a patient population or other factor that significantly increases the risks (or decreases the acceptability of the risks) associated with the use of the drug product; 3) The investigation is not intended to be reported to FDA as a well-controlled study in support of a new indication for use nor intended to be used to support any other significant change in the labeling for the drug; and 4) The investigation is not intended to support a significant change in the advertising for the product.

The lozenges will be stored according to the instructions on the box. They will be locked up inside the PI/PI-designee's office. Only IRB-approved members of the research team, Tobacco Treatment Specialists or physicians will provide NRT to the participants. Participants will be asked about any FDA contraindications at the time of dispersion. For all sites, the lozenges will be purchased by UMMS from a commercial vendor and mailed to each site as required. For Northwell Health and RMG, the lozenges will be kept locked in the site-PI-designee's office. For VACWM, the lozenges will be stored according to the instructions on the box and will be kept at the VACWM pharmacy. Only physicians listed as study staff will be able to prescribe NRT to the participants. Additionally, a copy of the participant's informed consent form will be uploaded to the participant's electronic medical record prior to dispensation of NRT.

Participants can choose to use or not to use the NRT. It will be provided to participants, but use of it is optional. A dispensation log will be kept at each site detailing the NRT that was provided to participants and the research staff member dispensing the lozenges. If participants use the NRT, they will be asked to participate in a smoking cessation verification test using a carbon monoxide (CO) monitor. At the conclusion of the project, unused NRT will be returned to study staff at UMMS for proper disposal if desired by participants. All returned NRT will be destroyed by the UMMS IDS pharmacy.

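### The 6-month cessation outcome is named as biochemically verified, but section 11 limits CO testing to users of the optional NRT and Hypothesis 4 is analysed on self-report with no CO rule

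*Combined protocol and SAP*

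**What the plan says.** **The outcome as named.** Section 3, Aim 3, lists "6-month biochemically verified point prevalent cessation" among the things to be evaluated. Table 3 in section 11 annotates smoking cessation as "biochemically verified a 3wk, 6 months". Neither place restricts who is tested.

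**Who is tested.** Three places deal with this.
- Section 11, under Aim 3 follow-up: "Biochemically verified smoking cessation tests will only be conducted with participants that used the optional NRT".
- Section 32: "If participants use the NRT, they will be asked to participate in a smoking cessation verification test using a carbon monoxide (CO) monitor". This implies the same limit without saying that others are excluded.
- Section 10, in the description of weeks 2-3: current smoking is determined by self-report plus CO verification, done at the recruiting site at the participant's final in-person session. No NRT condition is attached.

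On the lozenges, section 10 says: "It will be provided to participants, but use of it is optional".

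**What is analysed.** Section 12 says that cessation is assessed at follow-up surveys. It builds H4 on the question "Do you currently smoke cigarettes (smoked even 1 puff in the last 7 days", compared between arms by a chi-square test. It gives no rule for combining CO results with self-report or for classifying claims that were not tested. Section 10 allows a mailed 6-month survey when a participant cannot attend, and that yields no breath sample.

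**Status of H4.** The power analysis treats H1 and H3 as the two primary hypotheses, so H4 is secondary. For H4 it states: "A sample size of 200 in each group will achieve 80% power to detect a difference of 11" percentage points.

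**The concern.** The plan names one outcome, provides for measuring it in a subgroup, and analyses a different one.

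A report that follows Aim 3's wording would attach the verified label to quit claims that nobody checked. A report that used only CO results obtained under the section 11 rule would rest on a group defined by lozenge use. That is a choice made after randomization, and it sits badly with the intent-to-treat principle in section 12. Site staff also lack one consistent instruction on who is to be offered the test.

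**Working it through.** **1. The passages side by side**

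| Place | Who is CO-tested | When |
|---|---|---|
| Section 3, Aim 3 | no limit stated | 6 months |
| Section 11, Table 3 | no limit stated | 3 weeks and 6 months |
| Section 10, weeks 2-3 | no NRT condition | final in-person session |
| Section 11, Aim 3 follow-up | NRT users only | not stated |
| Section 32 | request conditional on NRT use | not stated |
| Section 12, H4 | no CO result used | 6 months |

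Section 10 (mini-pilot paragraph) and Table 5 in section 24 both give three in-person sessions for Aims 2 and 3, and the 6-month visit is in person unless the participant cannot come. The final in-person session is therefore plausibly the 6-month visit. On that reading section 10 conflicts directly with section 11. On the other reading it describes the end-of-Break test and conflicts with section 11 at 3 weeks.

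**2. The plan's H4 power.** Inputs from section 12: 200 per arm, 15% vs 26%, two-sided 0.05, pooled Z-test.
- Pooled rate 0.205. SE under the null = √(2 × 0.205 × 0.795 / 200) = 0.0404.
- SE under the alternative = √((0.15 × 0.85 + 0.26 × 0.74) / 200) = 0.0400.
- Power = Φ((0.11 − 1.96 × 0.0404) / 0.0400) = 78.0%.

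The stated 80% is reached at a difference of 11.3 points, so it holds to rounding.

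**3. Size of the labelling gap.** Planned quits: 200 × 0.15 = 30 and 200 × 0.26 = 52, total 82. The documents give no NRT-use rate, so the share of quitters who did not use NRT is assumed.
- 20% non-use: 82 × 0.2 = 16 untested.
- 60% non-use: 82 × 0.6 = 49 untested.
- If 10% of smokers also misreport (assumed), claims are 200 × (0.235 + 0.334) = 114, of which 23 to 68 are untested.

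**4. Bias in H4 as written.** The test uses the survey answer only. The CO result does not enter, so the CO rule contributes zero bias.

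**5. If CO results did enter H4** (not proposed by the plan). Suppose true cessation is 15% in both arms, and NRT use is 80% in control and 90% in intervention, independent of quitting (all assumed).
- Count confirmed quits only: 0.15 × 0.8 = 12.0% vs 0.15 × 0.9 = 13.5%, a false difference of +1.5 points.
- Let untested claims stand, with 10% misreporting: 0.15 + 0.85 × 0.10 × 0.2 = 16.70% vs 0.15 + 0.85 × 0.10 × 0.1 = 15.85%, a false difference of −0.85 points.

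Both signs reverse if the use rates swap, and both vanish if use is equal. Neither size nor direction can be known from the documents.

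**6. Power under each choice of outcome** (same pooled formula).
- CO-confirmed, everyone eligible, untested claims counted as smoking, 80% attendance in both arms (assumed): 12.0% vs 20.8%, power 66%.
- Self-report with 5% misreporting in both arms (assumed): 0.15 + 0.85 × 0.05 = 19.25% vs 0.26 + 0.74 × 0.05 = 29.70%, power 68%.

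**The case against.** The analyst is not actually left with two outcomes. Section 12 gives the exact H4 question, says that cessation is assessed by survey, and never calls H4 verified. H4 is not one of the hypotheses called primary. Most figures above beyond the 82 quits and the 78% power rest on assumed rates. All of this stands, and it makes the defect one of labelling and consistency. It does not remove the defect: Aim 3 and Table 3 still promise a verified outcome that the section 11 rule cannot supply for everyone, and three sections still disagree on who is tested.

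A reader might infer more than the documents support:
- **That H4 is biased by selective verification.** The H4 test uses self-report, so it is not. Bias would arise only if CO results were brought in under the section 11 rule, which section 12 does not propose.
- **That section 10 concerns only the 3-week test.** Its reference to the final in-person session makes this doubtful.
- **That 6-month follow-up by telephone is planned.** The Table 4 row listing telephone pools 3 weeks and 6 months, and the specialist's week-3 call could account for it. Mail is the only alternative to the 6-month visit that section 10 states.

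The Aims 2 and 3 timeline announced in section 10 could not be read in the text available. It may settle when CO is measured; it is unlikely to supply an H4 classification rule.

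**Conclusion.** This is an internal contradiction in a secondary outcome, and it should be corrected. Unless every participant uses the lozenges and attends in person, following section 11 cannot deliver the outcome that Aim 3 names.

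The contradiction follows from the text alone and needs no assumption. Its practical size does need one: roughly 16 to 49 of 82 planned quits untested, for assumed non-use of 20% to 60% among quitters. The primary hypotheses do not use CO and are untouched. Should CO results be used under the present rule, any bias would be of unknown size and direction, because the plan gives neither NRT-use nor misreporting rates.

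**What to change.** Reconcile section 3 (Aim 3), section 10 (weeks 2-3), section 11 (Table 3 and the Aim 3 paragraph), section 12 (H4) and section 32 in one of two ways.

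**(a) Verify everyone who claims abstinence.** Remove the NRT-use condition from sections 11 and 32. Offer the CO test at the planned 3-week and 6-month in-person visits to every participant in either arm who reports 7-day abstinence, and align section 10 to this. State in section 12 whether H4 is self-reported or CO-confirmed, and how untested and mailed claims (and telephone claims, if any) are counted. Report the other version alongside, with tested and untested counts by arm.

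Cost:
- About 16 to 68 additional breath tests at 6 months if every claimant attends (the range in step 3), plus some at 3 weeks. Section 22 already provides for CO meters.
- Possible amendments at Northwell Health and VACWM, whose mirrored plans are approved by their own IRBs (section 21).
- Lower power if untested claims count as smoking, for example 78% to about 66% at an assumed 80% attendance in both arms.

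**(b) Keep the restriction and drop the label.** Define H4 as self-reported 7-day abstinence, remove the biochemical-verification wording from Aim 3 and Table 3, and align section 10 with the restriction. This matches the question already in section 12 and changes only text. The cost is that no verified cessation outcome exists for all participants. Unchecked misreporting would also dilute a real effect, with power about 68% at an assumed 5% in both arms.
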